Mindfulness and Parent Stress Reduction:
Improving Outcomes for Children With Autism
Spectrum Disorder

NCT03459625

16JUL2018

PROTOCOL

PROJECT INFORMATION

Project Title: Mindfulness Awareness for Parenting Stress (MAPS) Project for Parents of Children with Developmental Delays

Funding: Funding comes from [name] start-up research funds that she received as part of her package at Loma Linda University

Phase of Study: This is the first phase of MAPS study and the first IRB application that has been submitted for this study.

PRINCIPAL INVESTIGATOR'S INFORMATION

Principal Investigator: [name].

- Address: Loma Linda University, Department of Psychology, [name]
- [contact]
- Email: [contact]

STUDY PERSONNELL

All other personnel are currently doctoral students in the Ph.D. or Psy.D. Clinical Psychology programs at Loma Linda University. Their names are listed below and their certificates certifying that they have completed the human subjects training are also include in this application.

Name	Doctoral Program at LLU	Year in Program
[name]	Ph.D. in Clinical Psychology	2 nd
[name]	Psy.D. in Clinical Psychology	2 nd
[name]	Psy.D. in Clinical Psychology	2 nd
[name]	Ph.D. in Clinical Psychology	3 rd
[name]	Ph.D. in Clinical Psychology	1 st
[name]	Ph.D. in Clinical Psychology	1 st
[name]	Psy.D. in Clinical Psychology	2 nd

STUDY INFORMATION

The MAPS Project is a low-risk social/behavioral study that examines the efficacy of a stress-based intervention for parents of children with developmental delays (see description below for more detail). Laboratory assessments will take place in [name] laboratory in the Psychology Department ([name], Rooms 5 and 6). The intervention will be delivered at the Behavioral Health Institute ([name]).

Timeline for the study is as follows:

	Oct '11	Nov '11	Dec '11	Jan '12	Feb '12	Mar '12	April '12	May '12	June '12	July '12	Aug '12	Sept '12
Recruitment (N=90)	X	X	X	X	X							
Pre- Intervention Group Assessments for Spring and Summer Groups (N=90)		X	X	X	X							
Spring Group Intervention (N=45)						X	X					
Post- Intervention Assessments for Spring Group (N=45)								X				
Second Pre- Intervention Assessment for Summer Group (N=45)									X			
Summer Group Intervention (N=45)									X	X		
Post- Intervention Assessments for Summer Group (N=45)											X	

NOTE: Follow-up assessments will be conducted after 6 months post-intervention. They will occur in November 2012 for the Spring group and in February 2013 for the Summer group.

INCLUSION/EXCLUSION CRITERIA

All individuals invited to participate in the study will be parents of children with developmental delays and clinically significant behavior problems. When there are two parents in the family, both parents will be invited to participate in the study; however, two parents from the same family will only count as one family. In other words, we plan to recruit the parent(s) of 90 children with developmental delays. Criteria for study entry are: (1) Having a child ages 3 to 5, (2) child has been determined by Regional Center (or by an independent assessment) to have a developmental delay, (3) parent(s) report more than 10 child behavior problems (the recommended cutoff score for screening children for treatment of conduct problems) on the Eyberg Child Behavior Inventory (ECBI; Robinson, Eyberg, & Ross, 1980), (4) the parent(s) is not receiving any form of psychological or behavioral treatment at the time of referral (e.g. counseling, parent training, parent support group, etc.), (5) parent(s) agree(s) to participate in the intervention (this requirement will be determined based on whether the parent(s) signs the consent form), and (6) parent(s) must speak and understand English.

Exclusion criteria include parents of children with debilitating physical disabilities or severe intellectual impairments that prevent them from participating in the assessment tasks described in the protocol (e.g. child is not ambulatory). As mentioned above, the child is only involved in the assessment aspects of the study pre-intervention, post-intervention, and at follow-up. During these assessments the child is instructed to play on the floor with the parent for 25 minutes. This task requires the child to understand the researcher's directions, sit-up on his/her own, explore different toys in the room, and interact with the parent. Therefore, if the child has a physical disability or severe intellectual impairment that prevents him or her from participating in the play task the family will be excluded from the study.

Robinson, E. A., Eyberg, S. M., & Ross, A. W. (1980). The standardization of an inventory of child conduct problem behaviors. *Journal of Clinical Child Psychology*, 9, 22-29.

SUBJECT RECRUITMENT & SCREENING

The goal is to recruit 90 families during the first 5 months of the study (October through February). When there are two parents in the family, both parents will be invited to participate in the study; however, two parents from the same family will count as one family. In other words, we plan to recruit the parent(s) of 90 children with developmental delays. We anticipate that about 20% of the sample will not complete the intervention leaving a total sample of about 70 families for the complete study. According to power calculations, sample size of 70 is sufficient to detect a medium size effect with a power of .80, giving us an 80% chance of detecting a significant effect if it is there.

Participants will be limited to parents of children ages 3 to 5 who are English-speaking. The rationale for the age restriction is that parents of children often exhibit heightened stress during the preschool years, while simultaneously experiencing a reduction in services because Early Start services in California terminate when the child is 3 years of age ([name], Green, & Baker, in press).

This intervention is targeted for this specific risk group. Additionally, all parents must speak and understand English because the Principal Investigator who will be delivering the intervention is monolingual English speaking. Other than these two restrictions, recruitment will be open to parents of all races/ethnicities, socio-economic classes, sexual orientations, and religions.

In terms of vulnerable subjects, this research primarily involves parents of children with developmental delays and elevated behavior problems. The research focuses on the questions of (1) how parental stress contributes to subsequent behavior problems in children with delays and (2) how reducing parental stress and promoting parent's mental health impacts children's behavior over time. Children will only be asked to participate in a 25-minute play assessment pre and post-intervention as well as at the follow-up assessment. This study is minimal risk to children and their families.

Subjects will be primarily recruited through the Inland Empire Regional Center. The Principal Investigator (PI) has established collaborations with Regional Center and the Director of the agency, [name], has committed to helping [name] recruit participants for the MAPS study (see enclosed letter from Regional Center). Families who meet the study criteria will be identified from the Regional Center's computerized data bases, and screened by agency staff. In order to protect confidentiality, letters to prospective families will be sent by the Regional Center staff, informing parents about our project (We have enclosed a sample letter). Interested parents will either contact the MAPS project by phone, return a postcard requesting us to contact them, or submit their contact information on the MAPS website. If the family indicates interest in participation the PI or her staff will conduct a phone screen (please refer to enclosed phone screen document). If the family meets eligibility for the study, an appointment will be scheduled for the initial laboratory assessment.

[name], Green, S., Baker, B.L. (in press). Relationship between parenting stress and child behavior problems: An examination across time. *Journal of Intellectual and Developmental Disabilities*.

INFORMED CONSENT PROCESS

Informed consent will be obtained at the first laboratory assessment. Parents will be given the informed consent form (see included consent form) and asked to read the form. If the parent prefers, the experimenter will read the form to the parent. The experimenter will also provide a summary of study (e.g. timeline for intervention, expectations with regard to pre, post and follow up assessments, compensation, components of assessment, and potential risks of study). Parents will be informed that intervention group assignment is random and that they may be assigned to the Spring group (March through April 2012) or the Summer group (June through July 2012). The experimenter will be available to answer any and all questions the parent(s) has and to address any concerns. Parents will be reminded that their consent is voluntary, that they can withdrawal from the study at any point, and that they do not have to answer any question or participate in any task that they do not want to. Given the young age of the children in the study (ages 3 to 5), parents will consent for their own and their child's participation. The PI for this project has had extensive training in conducting research with similar families and has completed the HIPAA compliance training online (certificate is included). Graduate students working on

the project as research assistants have also completed the HIPAA training online and are completing training with the PI on providing informed consent and administering the standardized protocol.

STUDY DESIGN

Background. Parents of children diagnosed with developmental delays consistently report higher levels of parenting stress compared to parents of typically developing children (Dyson, 1993). These parents are faced with many challenges across their child's lifespan, including overcoming the disappointments related to the original diagnosis, securing school placements, and learning to navigate the health and educational systems (Glidden 1989; Floyd et al. 1996; Chen & Tang 1997). As a result, parents of children diagnosed with developmental disabilities are likely to have ongoing and new stressors that maintain and even increase stress levels across time, suggesting the stress of parents of children with developmental disabilities can be chronically high. Elevated stress levels are a concern because studies indicate that elevations in stress among parents of children with developmental disabilities are associated with anxiety, depression, and other mental health problems (Olsson & Hwang, 2001; Yirmiya & Shaked, 2005) as well as poor physical health, particularly in with respect to cardiovascular, immune, and gastrointestinal systems (Miodrag & Hodapp, 2010).

Additionally, research conducted by the PI of the MAPS Project, [name], and others indicates that parental stress and well-being have significant implications for children with developmental delays. [name] has shown that early elevations in parenting stress are associated with poorer social skills later in development ([name] & Baker, 2008), higher levels of behavior problems ([name], Green, & Baker, in press), as well as a later ADHD diagnosis (Baker, et al, 2010) among children with developmental disabilities. Furthermore, research indicates that the treatment of children with developmental delays may be compromised when parents are experiencing overwhelming levels of stress (Robbins, Dunlap, & Plienis, 1991).

Given the negative consequences of stress for parents and their children, we must provide support to parents as well as their children. The MAPS Project was developed to reduce parenting stress in order to improve parental well-being, thereby optimizing outcomes for children with delays. MBSR, the intervention delivered in the MAPS Project, is an evidence-based stress-reduction intervention program supported by over two decades of extensive research showing its effectiveness in reducing stress, anxiety, and depression, and promoting overall well-being (Chiesa & Serretti, 2009; Grossman, Niemann, Schmidt, & Walach, 2004). These studies indicate that the majority of people who complete the 8-week program report greater ability to cope more effectively with both short and long-term stressful situations, which are critical skills for parents of children with developmental delays. MBSR may also help to improve one's parenting experience. Mindfulness helps parents to slow down, notice impulses before they act, really listen to their children, and come to a more relaxed and peaceful state of mind, which in turn has a positive effect on children with developmental delays.

MBSR is an empirically-supported secular (non-religious) based intervention that can be beneficial to people of all backgrounds. The MBSR course offers intensive training in relaxation techniques, meditation, gentle Yoga-based stretching, lectures in various aspects of health and

wellness, and supportive group discussions. The program includes eight weekly 2.5 hour sessions, a day-long meditation retreat, daily home practice based on audio CDs with instruction, and daily record keeping of mindfulness exercises. The emphasis on Mindfulness, which simply means paying attention to each moment in a non-judgmental way, fosters a practical way to apply these methods in everyday life.

Although MBSR has not been evaluated as an intervention for parenting stress, studies have supported the efficacy of other mindfulness interventions with parents, suggesting that this type of intervention is feasible and effective with this population. More specifically, “mindful parenting” interventions have been found to be effective in reducing children’s externalizing behaviors and attention problems as well as improving children’s self-control, compliance, and attunement to others (Singh et al., 2010). This is a manualized parenting intervention that incorporates mindfulness, self-awareness, and intentionality. In contrast to MBSR where the focus is on the parents’ personal stress, the focus of this approach is on the parent-child relationship and the intervention teaches parents to identify interactions that result in relational disconnectedness (Placone-Willey, 2002). This intervention has been used with the parents of typically developing children with externalizing behavior problems as well as children with autism (Singh et al., 2006). These studies support the efficacy of using mindfulness interventions for parents; however, they generally have small samples and lack random assignment or control groups, suggesting there is still a clear need for research in this area.

In addition to hopefully helping families cope with children’s behavior more effectively, this study is also important because it is a rigorous, experimental test of the PIs theoretical model. This study will experimentally manipulate parenting stress and then look for subsequent changes in child behavior problems. If there are changes, this provides stronger evidence that parenting stress has an effect on the development of children’s behavior problems.

Baker, B.L., [name], Fenning, R., Crnic, K. A., & Blacher, J. (2010). Mental disorders in five year old children with or without intellectual disability: Focus on ADHD. *Journal of Child Clinical and Adolescent Psychology*, 49, 492-505.

Boyd, B. A. (2002). Examining the relationship between stress and lack of social support in mothers of children with autism. *Focus on Autism and Other Developmental Disabilities*, 17(4), 208-215.

Chen, T. Y., & Tang, C. S. (1997). Stress appraisal and social support of Chinese mothers of adult children with mental retardation. *American Journal on Mental Retardation*, 101, 473-482.

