Sanders, J. L., & Morgan, S. B. (1997). Family stress and adjustment as perceived by parents of children with autism or down syndrome: Implications for intervention. *Child & Family Behavior Therapy*, 19(4), 15-32.

Singh, N. N., Lancioni, G. E., Winton, A. S. W., Fisher, B. C., Wahler, R. G., McAleavey, K., . . . (2006). Mindful parenting decreases aggression, noncompliance, and self-injury in children with autism. *Journal of Emotional and Behavioral Disorders*, 14(3), 169-177.

Singh, N. N., Lancioni, G. E., Winton, A. S. W., Singh, J., Singh, A. N., Adkins, A. D., & Wahler, R. G. (2010). Training in mindful caregiving transfers to parent-child interactions. *Journal of Child and Family Studies*, 19(2), 167-174.

Yirmiya, N., & Shaked, M. (2005). Psychiatric disorders in parents of children with autism: A meta-analysis. *Journal of Child Psychology and Psychiatry*, 46(1), 69-83.

Objectives

Aim 1: To determine whether MBSR is a feasible intervention with parents of children with developmental delays.

- Hypothesis: The majority of parents (minimum of 60%) who enter the program complete the full 8 weeks of the program. Although we hope for less attrition, this is a conservative estimate given that attrition from child psychotherapy in general is high, ranging from 40% to 60% (Wierzbicki & Pekarik, 1993).

Aim 2: To examine whether MBSR leads to reductions in parenting stress.

- Hypothesis: Parents will self-report significantly lower levels of stress post-intervention and at follow-up.

Aim 3: To investigate whether MBSR is associated with changes in parenting behavior.

- Hypothesis: Parent receiving the intervention will exhibit less negative and intrusive behavior and more positive and sensitive behavior compared to controls as evidenced in observational as well as self-report measures.

Aim 4: To determine whether reductions in parenting stress are associated with decreases in child behavior problems at post-intervention and at follow up.

- Hypothesis: Children of parents receiving MBSR will show greater reductions in behavior problems compared to children of waitlisted parents as evidenced by the participating parent, spouse/significant other, and teacher reports.

Aim 5: To evaluate whether parenting behavior mediates the relationship between parenting stress and child behavior problems.

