Parents assigned to the spring group will begin intervention in March and parents assigned to the summer intervention will begin intervention in June. The intervention will follow the MBSR manual outlined by [name] (Kabat-Zinn et al., 1992). The intervention consists of three main components: (1) didactical material covering the concept of mindfulness, the psychology and physiology of stress and anxiety, and ways in which mindfulness can be implemented in everyday life to facilitate more adaptive responses to challenges and distress, (2) mindfulness exercises during the group meetings and as homework between sessions, and (3) discussion and sharing in pairs and in the larger group. The MBSR program includes eight weekly 2.5 hour sessions, a day-long meditation retreat after class 6, and daily home practice based on audio CDs with instruction. Formal mindfulness exercises include the body scan, sitting meditation with awareness of breath, and mindful movement. MBSR is an empirically supported secular (non-religious) based intervention that can be beneficial to all people. The PI has undergone formal training in MBSR through InsightLA (<http://www.insightla.org>) and has multiple collaborations with formal MBSR teachers. Currently, [name] is planning to deliver the intervention herself; however, if funding permits she will hire a certified MBSR teacher (who will complete HIPAA certification and obtain IRB approval before teaching).

After the completion of the project (all assessments have been conducted) parents will receive a short summary of their child's current and previous behavioral functioning in order to reinforce parents' efforts to improve their parenting skills as well as raise awareness of remaining concerns.

Robinson, E. A., & Eyberg, S. M. (1981). The dyadic parent-child interaction coding system: Standardization and validation. *Journal of Consulting and Clinical Psychology*, 49(2), 245-250.

Measures and Data Collection

See table below for information on measures and data collection time points (pre-intervention, post-intervention, and follow-up)

Measures for MAPS Program (Mindful Awareness & Parenting Stress)

Measure	Pre-Tx	Post-Tx	Follow-Up	Description	Type of Measure

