With regard to questionnaires, for the NIH grant we have added a few parent questionnaires. More specifically, we have included a revised version of the Parenting Stress Index (we are now using the 4th edition instead of the 3rd edition that we used on MAPS), the Social Communication Questionnaire, Attachment Q-Sort questionnaire, Beck Anxiety Inventory, Behavioral Inhibition Questionnaire, Preschool Anxiety Questionnaire, Repetitive Behavior Scale-Revised, Family Resource Scale, Parenting Scale, and Parental Flooding Scale. We have also added one teacher-report questionnaire, the Preschool Anxiety Questionnaire-teacher report version. All of these measures are psychometrically sound and have been frequently used with families of young children with developmental delays and Autism Spectrum Disorder.

b. Classification of significant change(s):

- SAFETY

1a. List any change(s) in monitoring (number each change):

1b. If any item(s) listed above DECREASE monitoring, explain why subject safety will NOT be adversely affected.

- PROCEDURES

2a. List any change(s) in subject-related intervention (number each change): None
2b. What is the scientific justification for item(s) above, and explain how risk to subjects is affected:

There is no additional risk to subjects. The changes are scientifically justified because the revised changes to the phone screen, consent, and questionnaires will more accurately identify the families eligible for this study (phone screen), provide more accurate information to participants about what the study will entail (consent), add additional psychometrically sound measures to assess the constructs of interest, and is in line with the NIH funded proposal.

SUBJECTS

3a. List any change(s) that remove exclusion criteria or broaden inclusion criteria (number each change): The study will now focus on children with Autism Spectrum Disorder specifically, rather than children with developmental delays more broadly.

3b. Justify any item(s) above that remove safety exclusion or modifies fairness in subject selection: This is what was approved by NIH for this project.

ADMINISTRATIVE

4a. Change study title of IRB approval to the following: Stress-reduction techniques for effective parenting skills (STEPS) project

4b. If study personnel will be changed, use the "Request to Change IRB Study Personnel" form.

4c. If sponsor has changed, name of sponsor is:

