If yes: "Great! Before I go over all of the study details, I would like to point out that this particular intervention is for parents of children with ASD. Is your child currently diagnosed with an autism spectrum disorder?"

Complete Section I

If yes:

"If you have a few minutes, I'd like to tell you a little more about this study. Is now a good time?"

If no:

Explain that we're only recruiting children with an ASD diagnosis at this time so they will not be eligible for the study but we plan on having more groups for parents of children with developmental delays. Ask if they would like to be placed on the waitlist to be contacted for the next study. Thank them for reaching out and for taking the time to hear about the study. After hanging up, add family to the waitlist and input all of the necessary info.

2. Brief Summary of the Intervention:

"The STEPS Project is an intervention study taking place at Loma Linda University in collaboration with Cal State Fullerton for parents of children with autism spectrum disorder. It was put in place to provide support for parents and to reduce parenting stress. Our hope is that this experience will help reduce your parenting stress, enable you to feel more confident as a parent, reduce concerns you have about your child, and in turn, improve your child's behavior.

As a part of this study, you would participate in one of two parent interventions. One intervention focuses on mindful awareness and the other is an educational parent support group. Both groups run for 8 weeks and have one 6-hour weekend event during week 6. If you choose to enroll in the program, it will be very important for you to attend all 8 intervention sessions and the weekend event. Childcare will be provided. Groups will be either Monday or Wednesday night and both will begin mid-January 2019 and end in March 2019. You will be randomly assigned to a group, like the flip of a coin. We will let you know which group you will be assigned to after your first lab assessment.

As I said, we are offering these interventions as part of a research study and therefore, in order to determine how effective the treatments are, we are asking that families participate in five lab visits for assessments. There will be two before the group begins, one immediately after the group is completed, one 6 months after the group is done, and one 12 months after the group is done.

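### Under the MAPS timeline the waitlist arm is treated before any follow-up visit, so Aim 4's waitlist comparison exists only at post-intervention; the aims and analysis were not updated to the 2018 two-group design

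*Combined protocol and SAP*

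**What the plan says.** **MAPS protocol, 2011–2013 text.** The Study Information timeline shows the Spring course in March–April 2012 and Spring post-assessment in May. Summer has a second pre-intervention assessment in June, its course in June–July and its post-assessment in August. Procedures confirms that "parents assigned to the summer intervention will begin intervention in June". The note under the timeline puts follow-up six months after the intervention: "They will occur in November 2012 for the Spring group and in February 2013 for the Summer group".

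**Aims.** Aim 2's hypothesis is "Parents will self-report significantly lower levels of stress post-intervention and at follow-up". It names no comparator. Aim 4's opening sentence asks whether stress reductions go with fewer child behaviour problems at post-intervention and at follow-up. Its hypothesis is "Children of parents receiving MBSR will show greater reductions in behavior problems compared to children of waitlisted parents", with no time point. Aim 3 compares with controls and names no follow-up.

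**Analysis.** For both parenting stress and child behaviour, Data Analysis asks whether there is a reduction resulting from the intervention and gives dependent-sample t-tests as the example. It names no between-arm test for either outcome. Hierarchical linear modelling is mentioned only as a possibility.

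**2018 materials.** The phone screen instructions (Brief Summary of the Intervention) say: "One intervention focuses on mindful awareness and the other is an educational parent support group". Both groups start in mid-January 2019. There are two visits before the group, one just after it, and one each at 6 and 12 months. Item 2a of the Change Request Form reads: "List any change(s) in subject-related intervention (number each change): None".

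**The concern.** A waitlist is a control only while it waits. If it has been treated by the time of follow-up, the randomised comparison then sets treated families against treated families and says little about whether MBSR works. The remaining evidence is each family's change from baseline, which mixes any effect of the programme with ageing of the child, regression to the mean and other events.

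Regression to the mean is a realistic worry. MAPS entry requires more than 10 behaviour problems on the ECBI, so children are selected for high scores on an outcome measure. The Background also faults earlier mindfulness-parenting studies for lacking randomisation or control groups and presents this trial as an experimental test. A durability claim from paired tests would have the weakness that the protocol criticises.

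The 2018 materials raise a second problem. They describe a different comparator, under which the waitlist wording in the aims no longer refers to any group in the trial.

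**Working it through.** **1. The plan's own dates.** Counting from the post-assessment month: Spring, May 2012 + 6 = November 2012; Summer, August 2012 + 6 = February 2013. Both stated follow-up dates reproduce. Counted from the last month of the course (April, July), each is 7 months.

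**2. Who is untreated, and when.**

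| | Spring arm | Summer arm |
|---|---|---|
| First pre-assessment | Nov 2011–Feb 2012 | Nov 2011–Feb 2012 |
| Course | Mar–Apr 2012 | Jun–Jul 2012 |
| Controlled contrast | post, May 2012 | second pre, June 2012 |
| Own post-assessment | May 2012 | Aug 2012 |
| Follow-up | Nov 2012 | Feb 2013 |

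Summer starts its course 5 months, and ends it 4 months, before the first follow-up visit (June to November; July to November). Its last untreated assessment is June 2012, one month after Spring's post-assessment and in the month its own course begins. It has no untreated assessment at or after November 2012.

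**3. What a between-arm follow-up contrast would estimate.** It estimates the benefit remaining in Spring minus the benefit remaining in Summer, each 6 months after its own post-assessment. If benefit persists equally in both arms, this is 0 whether or not MBSR works, and a 5% test rejects 5% of the time. If persistence differs, the contrast is not zero, but it still does not compare MBSR with no MBSR.

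**4. Power where the controlled contrast exists (illustration).** Assumed: d = 0.5, two-sided 5%, two-sample t-test. The noncentrality is d × √(n/2), with n per arm.
- n = 45 (all enrolled): 0.5 × √22.5 = 2.37, power 65%.
- n = 35 (70 completers in two equal arms): 0.5 × √17.5 = 2.09, power 54%.

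**5. What a paired test does with drift alone (illustration).** Assumed: 70 families pooled, no MBSR effect, an improvement of 0.1, 0.2 or 0.3 SD between baseline and follow-up, and baseline–follow-up correlation r of 0.5 to 0.7. The documents give none of these drift or correlation values. The SD of change is √(2(1 − r)), so the noncentrality is drift × √70 / √(2(1 − r)). Example: r = 0.5 and drift 0.2 give 0.2 × 8.37 / 1 = 1.67.

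| Drift | Significant reduction declared, r = 0.5 to 0.7 |
|---|---|
| 0.1 SD | 13% to 19% |
| 0.2 SD | 38% to 57% |
| 0.3 SD | 70% to 89% |

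The interval over which drift could act is 9–12 months for Spring (November–February to November). For Summer it is 12–15 months from the first pre-assessment, or 8 months from the second (June 2012 to February 2013).

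**6. The 2018 design.** Both groups start together, both receive something, and both are seen just after the group and at 6 and 12 months. A randomised contrast is available at all three visits. The aims and Data Analysis do not describe it.

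**The case against.** Several stronger readings are tempting, and the documents do not support them.

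- **That Aim 2 promises a waitlist comparison at follow-up.** It names no comparator and is consistent with within-person change. Its weakness is lack of control, not an impossible contrast.
- **That Aim 4 states such a comparison outright.** Its time points and its waitlist comparator are in separate sentences. The time-point sentence concerns an association, which needs no untreated arm, and the hypothesis can be met at post-intervention. Joining the two is the natural reading, since Aim 4 has no other hypothesis for follow-up, but it remains a reading.
- **That the waitlist design has no usable control.** It has one, at post-intervention.
- **That item 2a shows the waitlist design still governs.** The phone screen in the same 2018 package describes another comparator. The change request also refers to revised aims reflected in the consent form, which was not part of the text reviewed. Updated aims may therefore exist outside the Objectives section.
- **That drift must favour MBSR.** The Background says that stress in these parents can be maintained or even rise. Upward drift would hide a benefit instead of creating one.

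All of these objections stand. The dates also stand, as does the mismatch between the Objectives and Data Analysis on one side and the 2018 comparator on the other. The statistical tests in Data Analysis are offered as examples, so a better analysis is not excluded. It is simply not specified.

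**Conclusion.** The point holds in a limited form. Under the MAPS timeline no untreated arm remains at either follow-up visit, so a comparison with waitlisted families is possible only at Spring post against Summer second pre-assessment, one month apart. Follow-up findings for Aims 2 and 4 would be uncontrolled, and attributing them to the intervention on the basis of dependent-sample t-tests would be unsound. This rests on the protocol's own dates and needs no assumption.

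The zero between-arm difference at follow-up is conditional on benefit persisting equally. The power figures (65% and 54%) and the paired-test rates are illustrations under assumed values.

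If the 2018 design governs, a controlled follow-up contrast is available. The defect is then that the aims, the analysis text and item 2a do not match the trial being run. It should be corrected, and the correction is mostly wording.

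**What to change.** 1. Reconcile the Objectives, timeline, Data Analysis, phone screen and change request, and state which design governs.
2. If the 2018 two-group design governs, replace the waitlist wording in Aim 4, and the controls in Aim 3, with MBSR versus support group by assigned arm. Make that between-arm contrast the analysis at post, 6 months and 12 months in place of dependent-sample t-tests. Correct item 2a.
3. For any data from the waitlist design, confine Aim 4's waitlist comparison to Spring post versus Summer second pre-assessment, analysed between arms. Report every follow-up result, including Aim 2's, as uncontrolled change. Rescheduling a 2012 visit is not an option in a document dated July 2018, so the one-month gap should be reported as a limitation.

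The cost is redrafting the aims, the analysis section and one form item. No extra visits or families are needed. The downside is that the waitlist design can support no controlled claim about follow-up.
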